### **5.6.1 Acceptable Concomitant Medications**

All treatments that the investigator considers necessary for a subject's welfare may be administered at the discretion of the investigator in keeping with the community standards of medical care. All concomitant medication will be recorded on the case report form (CRF) including all prescription, over-the-counter (OTC), herbal supplements, and IV medications and fluids. If changes occur during the trial period, documentation of drug dosage, frequency, route, and date may also be included on the CRF.

All concomitant medications received within 28 days before the first dose of trial treatment and 30 days after the last dose of trial treatment should be recorded. Concomitant

medications administered after 30 days after the last dose of trial treatment should be recorded for SAEs and ECIs as defined in Section 7.2.

### **5.6.2 Prohibited Concomitant Medications**

Subjects are prohibited from receiving the following therapies during the Treatment Phase of this trial:

- Antineoplastic systemic chemotherapy or biological therapy
- Immunotherapy not specified in this protocol
- Chemotherapy not specified in this protocol
- Investigational agents other than pembrolizumab
- Radiation therapy
  - Note: Radiation therapy to a symptomatic solitary lesion or to the brain may be allowed at the investigator's discretion.
- Live vaccines within 30 days prior to the first dose of trial treatment and while participating in the trial. Examples of live vaccines include, but are not limited to, the following: measles, mumps, rubella, varicella/zoster, yellow fever, rabies, BCG, and typhoid vaccine.
- Systemic glucocorticoids for any purpose other than to modulate symptoms from an event of clinical interest of suspected immunologic etiology. The use of physiologic doses of corticosteroids may be approved after consultation with the Sponsor.

Subjects who, in the assessment by the investigator, require the use of any of the aforementioned treatments for clinical management should be removed from the trial. Subjects may receive other medications that the investigator deems to be medically necessary.

The Exclusion Criteria describes other medications which are prohibited in this trial.

There are no prohibited therapies during the Post-Treatment Follow-up Phase.

Note: A supportive medication or vaccination that has been prospectively approved by the principal investigator, or administered for a medically urgent reason and then later approved by the principal investigator, at a point in time after the patient has met inclusion criteria and before administration of the medication nor vaccination in question, and the patient has started on the first pembrolizumab dose cannot count as a protocol violation for reason of a prohibited concomitant medication violation.

## 5.7 Rescue Medications & Supportive Care

### 5.7.1 Supportive Care Guidelines for events attributed to pembrolizumab

Note: Each adverse event will be attributed by the treating physician or the PI as follows:

- (1) Likely from pembrolizumab, but not to particularly to IL-2
- (2) Likely from IL-2, but not particularly to pembrolizumab
- (3) Likely from the combination of IL-2 and pembrolizumab
- (4) Not apparently related to either IL-2 nor pembrolizumab.

Subjects should receive appropriate supportive care measures as deemed necessary by the treating investigator. Suggested supportive care measures for the management of adverse events with potential immunologic etiology are outlined below and in greater detail in the ECI guidance document. Where appropriate, these guidelines include the use of oral or intravenous treatment with corticosteroids as well as additional anti-inflammatory agents if symptoms do not improve with administration of corticosteroids. Note that several courses of steroid tapering may be necessary as symptoms may worsen when the steroid dose is decreased. For each disorder, attempts should be made to rule out other causes such as metastatic disease or bacterial or viral infection, which might require additional supportive care.

The treatment guidelines are intended to be applied when the investigator determines the events to be related to pembrolizumab. The treatment of events that the investigator determines to be related to interleukin-2 may be managed in the usual manner, with no specific restrictions related to the participation in the protocol.

Note: If after the evaluation the event is determined to be not related, the investigator is instructed to follow the ECI reporting guidance but does not need to follow the treatment guidance (as outlined in the ECI guidance document). Refer to Section 5.2.1 for dose modification. For this trial, this particularly pertains to adverse events that are assessed to be usual events as described on the Proleukin™ prescribing information. ([www.proleukin.com](http://www.proleukin.com))

It may be necessary to perform conditional procedures such as bronchoscopy, endoscopy, or skin photography as part of evaluation of the event. Suggested conditional procedures, as appropriate, can be found in the ECI guidance document.

- **Pneumonitis:**

- For **Grade 2 events**, treat with systemic corticosteroids. When symptoms improve to Grade 1 or less, steroid taper should be started and continued over no less than 4 weeks.
- For **Grade 3-4 events**, immediately treat with intravenous steroids. Administer additional anti-inflammatory measures, as needed.
- Add prophylactic antibiotics for opportunistic infections in the case of prolonged steroid administration.

- **Diarrhea/Colitis:**  
Subjects should be carefully monitored for signs and symptoms of enterocolitis (such as diarrhea, abdominal pain, blood or mucus in stool, with or without fever) and of bowel perforation (such as peritoneal signs and ileus).
  - All subjects who experience diarrhea/colitis should be advised to drink liberal quantities of clear fluids. If sufficient oral fluid intake is not feasible, fluid and electrolytes should be substituted via IV infusion. For Grade 2 or higher diarrhea, consider GI consultation and endoscopy to confirm or rule out colitis.
  - For **Grade 2 diarrhea/colitis** that persists greater than 3 days, administer oral corticosteroids.
  - For **Grade 3 or 4 diarrhea/colitis** that persists > 1 week, treat with intravenous steroids followed by high dose oral steroids.
  - When symptoms improve to Grade 1 or less, steroid taper should be started and continued over no less than 4 weeks.
- **Type 1 diabetes mellitus (if new onset, including diabetic ketoacidosis [DKA]) or  $\geq$  Grade 3 Hyperglycemia, if associated with ketosis (ketonuria) or metabolic acidosis (DKA)**
  - For **T1DM or Grade 3-4 Hyperglycemia**
    - Insulin replacement therapy is recommended for Type I diabetes mellitus and for Grade 3-4 hyperglycemia associated with metabolic acidosis or ketonuria.
    - Evaluate patients with serum glucose and a metabolic panel, urine ketones, glycosylated hemoglobin, and C-peptide.
- **Hypophysitis:**

- For **Grade 2** events, treat with corticosteroids. When symptoms improve to Grade 1 or less, steroid taper should be started and continued over no less than 4 weeks. Replacement of appropriate hormones may be required as the steroid dose is tapered.
- For **Grade 3-4** events, treat with an initial dose of IV corticosteroids followed by oral corticosteroids. When symptoms improve to Grade 1 or less, steroid taper should be started and continued over no less than 4 weeks. Replacement of appropriate hormones may be required as the steroid dose is tapered.
- **Hyperthyroidism or Hypothyroidism:**

Thyroid disorders can occur at any time during treatment. Monitor patients for changes in thyroid function (at the start of treatment, periodically during treatment, and as indicated based on clinical evaluation), and for clinical signs and symptoms of thyroid disorders.

  - **Grade 2** hyperthyroidism events (and **Grade 2-4** hypothyroidism):
    - In hyperthyroidism, non-selective beta-blockers (e.g. propranolol) are suggested as initial therapy.
    - In hypothyroidism, thyroid hormone replacement therapy, with levothyroxine or liothyroinine, is indicated per standard of care.
    - *Note: hyper- and hypothyroidism may occur in relation to IL-2 as well. The discontinuation or continuation of pembrolizumab is at the discretion of the treating physician.*
  - **Grade 3-4** hyperthyroidism
    - Treat with an initial dose of IV corticosteroid followed by oral corticosteroids. When symptoms improve to Grade 1 or less, steroid taper should be started and continued over no less than 4 weeks. Replacement of appropriate hormones may be required as the steroid dose is tapered.
- **Hepatic:**
  - For **Grade 2** events, monitor liver function tests more frequently until returned to baseline values (consider weekly).
    - Treat with IV or oral corticosteroids
  - For **Grade 3-4** events, treat with intravenous corticosteroids for 24 to 48 hours.

- When symptoms improve to Grade 1 or less, a steroid taper should be started and continued over no less than 4 weeks.
- **Renal Failure or Nephritis:**
  - For **Grade 2** events, treat with corticosteroids.
  - For **Grade 3-4** events, treat with systemic corticosteroids.
  - When symptoms improve to Grade 1 or less, steroid taper should be started and continued over no less than 4 weeks.
  - *Note: Isolated elevation of creatinine occurring in relation to IL-2 administration should be evaluated over several days to assess if there is actually a nephritis or not, before committing to use of systemic corticosteroids.*
- **Management of Infusion Reactions:** Signs and symptoms usually develop during or shortly after drug infusion and generally resolve completely within 24 hours of completion of infusion.

Table 4 below shows treatment guidelines for subjects who experience an infusion reaction associated with administration of pembrolizumab (MK-3475).

Table 4 Infusion Reaction Treatment Guidelines

*Note: Every event, such as isolated hypotension or oliguria or elevation of creatinine should be critically evaluated for attribution to IL-2 or to pembrolizumab. Those occurring after IL-2 treatment should be expected to have resolved before the next pembrolizumab infusion, which is at least 6 days later.*

| NCI CTCAE Grade                                                                                                                                                                                | Treatment                                                                                                                                                                                                                                         | Premedication at subsequent dosing                                                                                                                                                                                                                      |
|------------------------------------------------------------------------------------------------------------------------------------------------------------------------------------------------|---------------------------------------------------------------------------------------------------------------------------------------------------------------------------------------------------------------------------------------------------|---------------------------------------------------------------------------------------------------------------------------------------------------------------------------------------------------------------------------------------------------------|
| Grade 1
Mild reaction; infusion interruption not indicated; intervention not indicated                                                                                                      | Increase monitoring of vital signs as medically indicated until the subject is deemed medically stable in the opinion of the investigator.                                                                                                        | None                                                                                                                                                                                                                                                    |
| Grade 2
Requires infusion interruption but responds promptly to symptomatic treatment (e.g., antihistamines, NSAIDS, narcotics, IV fluids); prophylactic medications indicated for <=24 hrs | Stop Infusion and monitor symptoms.
Additional appropriate medical therapy may include but is not limited to:
IV fluids
Antihistamines
NSAIDS
Acetaminophen
Narcotics
Increase monitoring of vital signs as medically | Subject may be premedicated 1.5h ( $\pm$ 30 minutes) prior to infusion of pembrolizumab (MK-3475) with:

Diphenhydramine 50 mg po (or equivalent dose of antihistamine).

Acetaminophen 500-1000 mg po (or equivalent dose of antipyretic). |

| NCI CTCAE Grade                                                                                                                                                                                                                                                                                                                                                                               | Treatment                                                                                                                                                                                                                                                                                                                                                                                                                                                                                                                                                                                                                             | Premedication at subsequent dosing |
|-----------------------------------------------------------------------------------------------------------------------------------------------------------------------------------------------------------------------------------------------------------------------------------------------------------------------------------------------------------------------------------------------|---------------------------------------------------------------------------------------------------------------------------------------------------------------------------------------------------------------------------------------------------------------------------------------------------------------------------------------------------------------------------------------------------------------------------------------------------------------------------------------------------------------------------------------------------------------------------------------------------------------------------------------|------------------------------------|
|                                                                                                                                                                                                                                                                                                                                                                                               | 
indicated until the subject is deemed medically stable in the opinion of the investigator.
 
If symptoms resolve within one hour of stopping drug infusion, the infusion may be restarted at 50% of the original infusion rate (e.g., from 100 mL/hr to 50 mL/hr). Otherwise dosing will be held until symptoms resolve and the subject should be premedicated for the next scheduled dose.
 
Subjects who develop Grade 2 toxicity despite adequate premedication should be permanently discontinued from further trial treatment administration.
                                                            |                                    |
| Grades 3 or 4 
Grade 3:
Prolonged (i.e., not rapidly responsive to symptomatic medication and/or brief interruption of infusion); recurrence of symptoms following initial improvement; hospitalization indicated for other clinical sequelae (e.g., renal impairment, pulmonary infiltrates)
 
Grade 4:
Life-threatening; pressor or ventilatory support indicated
 | 
Stop Infusion.
 
Additional appropriate medical therapy may include but is not limited to:
 
 
IV fluids
 
Antihistamines
 
NSAIDS
 
Acetaminophen
 
Narcotics
 
Oxygen
 
Pressors
 
Corticosteroids
 
Epinephrine
 
 
Increase monitoring of vital signs as medically indicated until the subject is deemed medically stable in the opinion of the investigator.
 
Hospitalization may be indicated.
 
Subject is permanently discontinued from further trial treatment administration.
 | No subsequent dosing               |
| Appropriate resuscitation equipment should be available in the room and a physician readily available during the period of drug administration.                                                                                                                                                                                                                                               |                                                                                                                                                                                                                                                                                                                                                                                                                                                                                                                                                                                                                                       |                                    |

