### **5.2.1.2 Dose Modification**

Adverse events (both non-serious and serious) associated with pembrolizumab exposure may represent an immunologic etiology. These adverse events may occur shortly after the first dose or several months after the last dose of treatment. Pembrolizumab must be withheld for pembrolizumab-related toxicities and severe or life-threatening AEs as per Table 3 below. See Section 5.6.1 and Events of Clinical Interest Guidance Document for supportive care guidelines, including use of corticosteroids.

In general, dose modifications of pembrolizumab are not required for events that appear to be directly related to interleukin-2 treatment and have resolved to a grade that is assessed as safe by the principle investigator, at the time of the next planned pembrolizumab treatment.

Table 3  
Dose Modification Guidelines for Drug-Related Adverse Events

| Toxicity                                                 | Hold Treatment For Grade | Timing for Restarting Treatment                                                                                                     | Discontinue Subject                                                                                                                                                |
|----------------------------------------------------------|--------------------------|-------------------------------------------------------------------------------------------------------------------------------------|--------------------------------------------------------------------------------------------------------------------------------------------------------------------|
| Diarrhea/Colitis                                         | 2-3                      | Toxicity resolves to Grade 0-1.                                                                                                     | Toxicity does not resolve within 12 weeks of last dose or inability to reduce corticosteroid to 10 mg or less of prednisone or equivalent per day within 12 weeks. |
|                                                          | 4                        | Permanently discontinue                                                                                                             | Permanently discontinue                                                                                                                                            |

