|                           | Grade 4                                                                                                                                                                                                                                                                                                                                                                                                                                                                                                                                                                                                                                                                                                                                                                                                                                                                                                                                                                                                      | Life threatening consequences; urgent intervention indicated.                                                                                                                                                                                            |

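### The suggested steroid trigger for pembrolizumab-attributed diarrhea/colitis is later for Grade 3-4 (more than 1 week) than for Grade 2 (more than 3 days)

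*Combined protocol and SAP*

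**What the plan says.** Section 5.7.1 has two adjacent bullets on steroids for diarrhea/colitis. Grade 2 that "that persists greater than 3 days, administer oral corticosteroids". Grade 3 or 4 "that persists > 1 week, treat with intravenous steroids followed by high dose oral steroids". Once symptoms fall to Grade 1 or less, a taper of at least 4 weeks follows. The same block asks sites to watch for signs of bowel perforation, and from Grade 2 upward to consider GI consultation and endoscopy.

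The guidelines apply once the investigator has judged the event related to pembrolizumab. They are introduced as suggestions: "Subjects should receive appropriate supportive care measures as deemed necessary by the treating investigator". Fuller detail is said to be in the ECI guidance document, which section 11.5 confirms is separate.

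Section 5.2.1.2 (Table 3) holds pembrolizumab for Grade 2-3 diarrhea/colitis and stops it permanently for Grade 4. For steroid use, its lead-in directs the reader elsewhere: "See Section 5.6.1 and Events of Clinical Interest Guidance Document for supportive care guidelines, including use of corticosteroids".

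**The concern.** A suggested trigger should not become slower as the event becomes more severe. Here a site that follows the text starts steroids later for severe or life-threatening colitis than for moderate colitis. The Grade 3-4 bullet includes Grade 4, which the grading table in 7.3.4 describes as "Life threatening consequences; urgent intervention indicated". A one-week persistence condition fits poorly with that description.

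What is at stake is patient management, not inference. Section 4.4.4.1 describes the trial as the first human experience of the two drugs together on this schedule, and section 4.5 says it is unknown whether the combination worsens immune-related effects. Sites are likely to lean on the written guidance in that setting.

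**Working it through.** No sample size, power or alpha figure is involved. The check has three steps.

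**1. The two triggers, both from 5.7.1**

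- Grade 2: more than 3 days, so the instruction applies from day 3 + 1 = day 4.
- Grade 3-4: more than 1 week = more than 7 days, so it applies from day 7 + 1 = day 8.
- Difference: 8 − 4 = 4 days, namely days 4 to 7.

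The gap concerns an event that is Grade 3-4 before Grade 2 steroids have begun. A patient already on steroids for Grade 2 is not told to stop if the event worsens.

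**2. The other Grade 3-4 steroid rules in 5.7.1**

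| Condition | Grade 3-4 steroid instruction | Persistence condition |
|---|---|---|
| Pneumonitis | "immediately treat with intravenous steroids" | None; immediate |
| Diarrhea/colitis | Intravenous, then high-dose oral | More than 1 week |
| Hypophysitis | Intravenous, then oral | None |
| Hyperthyroidism | Intravenous, then oral | None |
| Hepatic | "treat with intravenous corticosteroids for 24 to 48 hours" | None |
| Renal failure or nephritis | Systemic | None |

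Diarrhea/colitis is 1 of 6 with a wait. The renal entry carries a note to observe an isolated creatinine rise after IL-2 for several days before committing to steroids. That note settles attribution; it is not a wait that depends on grade.

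**3. Does any other text set the start time?**

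- Table 3 covers holding and stopping pembrolizumab. Its steroid wording concerns getting the dose down within 12 weeks, not when to begin.
- Section 5.6.1, where 5.2.1.2 sends the reader, is the list of acceptable concomitant medications and contains no steroid timing.
- Section 5.6.2 prohibits systemic glucocorticoids for any purpose "other than to modulate symptoms from an event of clinical interest of suspected immunologic etiology". It therefore permits earlier steroids but does not call for them.
- The ECI guidance document was not available for this review.

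Nothing in the document overrides the two triggers in 5.7.1.

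**The case against.** The strongest reply is that 5.7.1 is only an outline. The investigator may treat as needed, the introduction to 5.7.1 mentions oral or intravenous corticosteroids without limiting them by grade or duration, and the ECI guidance may give a different timing. This stands as a limit on the practical consequence. It does not repair the text: if the ECI guidance starts steroids earlier, the two documents conflict; if it agrees, the inversion still lacks an explanation.

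A second reply is that waiting leaves time to rule out infection or an IL-2 effect. But the guidelines apply after the event has been judged pembrolizumab-related, and any remaining work-up would be needed for Grade 2 as well. It cannot explain a longer wait for the worse grade.

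Third, four of the five comparator rules state no time at all; only pneumonitis says treatment is immediate. That is correct. The comparison is that none of the five has a persistence condition, not that all five state a wait of zero.

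Fourth, other safeguards operate meanwhile: fluids, consideration of GI consultation and endoscopy, the pembrolizumab hold or stop, the bar on IL-2 in the 5.2.4 checklist, and 24-hour reporting to the Sponsor of serious events (7.3.3.1). These reduce the risk but do not set the timing of steroids.

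Finally, this version is dated 03/16/2020, whereas enrollment was estimated to end in 3/2019 with 9 months of treatment, that is, until about 12/2019. If those estimates held, few or no patients would still have been on treatment. Actual dates are not given.

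**Conclusion.** The concern holds. As written, the Grade 3-4 trigger falls 4 days after the Grade 2 trigger, and it is the only one of six Grade 3-4 steroid rules in 5.7.1 with a persistence condition. The document gives no reason for the difference.

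The day count assumes that both durations run from the onset of the event. The practical effect depends on how far sites follow the suggestion and on what the ECI guidance says. The affected group is narrow: events attributed to pembrolizumab that reach Grade 3-4 before Grade 2 steroids have started. The endpoint analyses are untouched. The text should be corrected because a rule that gives a worse result when followed should not remain in safety guidance.

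**What to change.** Amend the Grade 3-4 diarrhea/colitis bullet in 5.7.1 so that its trigger is no later than the Grade 2 trigger. Two wordings achieve this:

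- Delete the one-week persistence condition, which brings the bullet into line with the other five Grade 3-4 steroid rules.
- As a minimum, use more than 3 days for both grades. This removes the inversion and leaves some time for infection work-up.

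The choice between them is clinical, and the clinical team should confirm it against the ECI guidance. In the same edit, point the corticosteroid cross-reference in 5.2.1.2 to 5.7.1 instead of 5.6.1; that part is clerical.

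The cost is one line and one cross-reference. Some patients may receive steroids earlier, and an event that would have settled within a week would then carry a taper of at least 4 weeks. IL-2 would be withheld during that time, because the 5.2.4 checklist bars it while steroids are in use for autoimmune problems. This cost is bounded: the checklist already bars IL-2 during any ongoing Grade 2 or worse event attributed to pembrolizumab, and Grade 4 colitis already ends pembrolizumab. The added delay falls mainly on Grade 3 events that have resolved.
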